Each patient's parent, legal guardian, or representative, must provide written informed consent prior to the patient's participation in the trial. The patient should provide assent, if capable of doing so. Each patient will enter a 4-week period during which the screening evaluations will be performed. Patients who meet the respiratory criteria for enrolment in the study in one of the first 3 weeks may have their screening period shortened. The screening assessments, which must be completed and results available prior to baseline, will consist of the following: a confirmation of the diagnosis of Rett syndrome, based on clinical criteria (a proven mutation of the methyl CpG-binding protein 2 (MECP2) gene is not required), a review of the patient's medical history and current use of medications, vital signs, 12-lead electrocardiogram (ECG), laboratory tests (hematology, blood chemistry, urinalysis, virology, serum pregnancy test for post-pubertal females, and thyroid function tests), physical and neurological examination. The patient's respiratory abnormalities will be documented, based on parental feedback for the presence of one of the following: periodic apnea during wakefulness; intermittent hyperventilation; breath holding spells; air swallowing; forced expulsion of air or saliva.

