9 INVESTIGATIONAL PLAN

9.1 Study Design

This is a prospective, 24-week, randomized, double-blind, placebo-controlled study designed to evaluate the safety, tolerability, and efficacy of multiple oral doses of sarizotan in patients with RTT with respiratory abnormalities. At least 129 patients will be randomized (approximately 43/group) to receive either low dose sarizotan (2 mg *bid* or 5 mg *bid*), high dose sarizotan (5 mg *bid* or 10 mg *bid*) or placebo *bid*. Patients 4 to <13 years of age will be randomized equally (1:1:1) to sarizotan 2 mg *bid* (low dose group), sarizotan 5 mg *bid* (high dose group), or placebo. Patients ≥ 13 years of age and weighing ≥ 25 kg will be randomized equally (1:1:1) to sarizotan 5 mg *bid* (low dose group), sarizotan 10 mg *bid* (high dose group), or placebo [Note: patients ≥ 13 years of age and weighing <25 kg will be eligible for the study, but will be included with the younger patients and randomized equally (1:1:1) to sarizotan 2 mg *bid* (low dose), sarizotan 5 mg *bid* (high dose) or placebo]. The paradigm for randomizing patients based on age and weight criteria is summarized schematically in Figure 4.

Figure 4. Randomization of patients to treatment according to age and body weight criteria

All patients 4 to <13 years of age, as well as those ≥ 13 years of age and weighing <25 kg, randomized to sarizotan 2 or 5 mg *bid* will start at a single dose of 2 mg on the morning of Day 1. Patients assigned to the 2 mg *bid* dose will remain on 2 mg once daily on Days 2-7, and will have their dose increased to 2 mg *bid* on Days 8-14. Patients assigned to the 5 mg *bid* dose will have their daily dose of sarizotan increased to 4 mg (2 mg *bid*) on Days 2-7, 7 mg (5 mg AM, 2 mg PM) on Day 8, and 10 mg (5 mg *bid*) on Days 9-14. Patients ≥ 13 years of age and weighing ≥ 25 kg randomized to sarizotan 5 or 10 mg *bid* will start at a single dose of 5 mg on the morning of Day 1, with an increase to 5 mg *bid* on Day 2. Patients randomized to 5 mg *bid* will continue on this dose for the rest of the study, while patients randomized to 10 mg *bid* will receive a single dose of 10 mg on Day 8 and have their dose increased to 10 mg *bid* on Day 9, and continue

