9.2.3 Documentation of Randomization

Only subjects who meet all of the inclusion criteria and none of the exclusion criteria for randomization are eligible for randomization into the treatment phase. In addition to violations of inclusion and exclusion criteria, reasons for randomization failure include a major protocol deviation, lost to follow-up, voluntary withdrawal, and study termination; the primary reason must be noted on the applicable CRF. Randomization will be on Day 1 at the start of dosing.

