On Day 1 the patient will be randomized to treatment, with the dose assigned based on age and body weight categories, as described in [Section 10.4](#), and will receive the initial oral dose of study medication (Dose Level 1: 2 or 5 mg sarizotan or matching placebo) in the morning. In the initial 12-hour period after the first dose, safety evaluations (vital signs, 12-lead ECG) will be performed at 1 and 4 hr post-dose. Blood samples for the pharmacokinetic (PK) analysis will be collected prior to dosing (blank sample) and at approximately 1 and 4 hr post-dose, following completion of the vital signs and ECG assessments. The patient will receive the evening dose (Dose Level 1: placebo for all patients) in the hospital (minimally 6 hours after the morning dose) and will be housed overnight, either in the hospital or with their parent/caregiver in a separate facility. The morning dose of Dose Level 2 (2 or 5 mg sarizotan or placebo, *bid*) will be administered on Day 2 in the clinic. Safety evaluations [vital signs, 12-lead ECG, laboratory tests (hematology, blood chemistry, urinalysis, and measurement of plasma ACTH and cortisol), physical/neurological examination, assessment of adverse events] will be repeated, and if no significant side effects are noted within the 4-hr period following this dose, the patient will be released from the hospital given a supply of study medication for the remainder of the first week of dosing at Dose Level 2 (Days 2 [PM] to 7) and for the second week of dosing at Dose Level 3 [2 mg sarizotan *bid*, 5 mg sarizotan *bid*, 7 mg sarizotan/day (5 mg in AM + 2 mg in PM), 10 mg sarizotan once daily (in AM, with placebo in PM) or placebo *bid*; on Day 8] and Dose Level 4 [2 mg sarizotan *bid*, 5 mg sarizotan *bid*, 10 mg sarizotan *bid*, or placebo *bid*; on Days 9 to 14].

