The mean rating of the caregiver-rated CIC at Week 24/endpoint will be compared between treatment groups using the Van Elteren test (a stratified Cochran Mantel Haenszel test with modified ridit scores). The following age strata will be considered in the analysis: <13 years and \geq 13 years. In addition to the above analysis, comparisons between treatments for the proportion of patients rated improved at Week 24 will be done using logistic regression.

Other Secondary Efficacy Outcomes

The analysis of the Caregiver Top 3 Concerns will be performed first, comparing the change from baseline in the total score on the VAS for each of the 3 symptoms identified as most concerning at baseline using an ANCOVA-LOCF analysis. The model will include treatment group and the baseline value along with age as covariates. Change will be estimated using the least-squares mean derived from the ANCOVA. Comparisons between treatment groups at Week 24 will be made using the difference in least-squares mean, 95% confidence interval (CI) and p-values from the ANCOVA model.

Descriptive statistics will be presented for the other secondary efficacy outcomes. The proportion of patients rated improved, as well as the mean score, on the Investigator-rated CGI-C at each of the scheduled visits will be presented. Actual values and the change from baseline in other secondary efficacy variables (Motor Behavioral Assessment Scale and subscales, other respiratory parameters, and RCSS) at all scheduled visits will be presented. An additional analysis of efficacy will be performed for patients with a sarizotan plasma concentration of >400 ng/mL.

Multiple Comparisons/ Multiplicity

The study level error rate will be controlled by following a sequential multiple testing procedure, where testing will begin with the primary efficacy endpoint. The effects of the high dose sarizotan versus placebo will be analyzed first for all parameters in a pre-specified sequence.

The sequence of testing will be as presented below:

- Percentage change from baseline in the number of apnea episodes,
- Mean rating of CIC,
- Mean change from baseline in the Top Three Concerns Total Score.

Initial 24-week Double-blind Treatment Period

The primary efficacy assessment for the study will be performed using data from the initial 24-week double-blind, placebo-controlled treatment period. A statistical “Win” will be claimed if the following results are obtained in the primary and key secondary efficacy analyses:

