6.5. COMMON CALCULATIONS

For quantitative measurements, change from baseline at Visit X will be calculated as:

$$\text{Value at Post-baseline Visit X} - \text{Baseline Value}$$

For quantitative measurements, percentage change from baseline at Visit X will be calculated as:

$$((\text{Value at Post-baseline Visit X} - \text{Baseline Value}) / \text{Baseline value}) * 100$$

Age will be calculated as following:

$$\text{Age} = (\text{Date of informed consent} - \text{Date of Birth} + 1) / 365.25$$

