15.1.4 KEY SECONDARY EFFICACY VARIABLE

The key secondary efficacy outcome was the difference between sarizotan and placebo on the Caregiver-rated Impression of Change (CIC) from baseline, a 7-point Likert-type scale for which ratings range from 1 = very much improved to 7 = very much worse, with 4 = no change. The key secondary efficacy analysis will be performed for the ITT population.

Summary statistics for CIC mean rating scores will be provided by visit and treatment group.

The mean rating of the caregiver-rated CIC at Week 24 LOCF will be compared between treatment groups using the Van Elteren test (a stratified Cochran Mantel Haenszel test with modified ridit scores). The following age strata will be considered in the analysis:

<13 years

>=13 years

Improvement on the CIC (i.e. Responder) will be defined as a Likert scale score of 1 (very

Document:	\\ieedc-vnasc01\BIOSdata\Newron\Sarizotan\PXA76395\Biostatistics\Documentation\SAP	Version Number:	V2
Author:	[name]	Version Date:	[30March2020]

Template No: CS_TP_BS016 – Revision 4
 Effective Date: 01Apr2016

Reference: CS_WI_BS005

much improved), 2 (much improved) or 3 (minimally improved). The proportion of patients with a rating of improvement in the CIC (n, count, and percent) will be presented at post-baseline visits by treatment group.

In addition to the above analysis, comparisons between treatments for the proportion of responders at Week 24 LOCF will be done using logistic regression. The logistic regression model will include treatment group and age. For the treatment comparison, an estimate of the odds ratio, corresponding Wald 95% CI and chi-square p-value will be presented.

Additionally, graphical presentation will be provided for the proportion of responders at Week 24.

In accordance with the original protocol (dated 27 October 2015, Section, page 70, Section 15.2.6) and the amended protocol (version 11.0, incorporating protocol Amendment 10, dated 29 November 2018, page 100, Section 15.2.6) as referred to in the FDA minutes of the meeting of February 5, 2020 issued by the FDA March 4, 2020, the Sponsor has reverted to using the “win” criteria referred to in these sections, as directed by FDA. A statistical “Win” will be claimed if the following results are obtained in the primary and key secondary efficacy analyses:

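### The CIC strata and the age subgroups split at 13 years alone, so patients aged 13 or over and under 25 kg are not analysed with the group they were randomised and dosed with

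*SAP*

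**What the plan says.** **Analysis.** SAP 15.1.4 compares the CIC at Week 24 (LOCF) between treatment groups with a Van Elteren test. It introduces the strata with "The following age strata will be considered in the analysis" and lists two: under 13 years, and 13 years or over. Protocol 15.2.6 has the same pair ("The following age strata will be considered in the analysis: <13 years and" 13 or over), and SAP Appendix 4 repeats it. SAP 7.5 uses the same cut for descriptive subgroups. Weight enters none of these.

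**Allocation.** Under protocol 11.2 patients are randomised on Day 1, "with the dose assigned based on age and body weight categories". Protocol 9.1 says that patients aged 13 or over who weigh less than 25 kg are eligible, "but will be included with the younger patients and randomized equally (1:1:1"; they go to 2 mg bid, 5 mg bid or placebo. SAP section 1 confirms the result: in these patients high dose means 5 mg bid and low dose means 2 mg bid. In patients aged 13 or over who weigh 25 kg or more, high dose is 10 mg bid and low dose is 5 mg bid.

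**Role of the CIC.** It is second in the testing sequence (SAP 7.4). The success rule at the end of SAP 15.1.4 asks only that it point in favour of high dose.

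**The concern.** A stratified test gains most when its strata are the groups within which patients were allocated and within which outcome and effect are most alike. Here one category of patients is allocated and dosed in one group and analysed in the other.

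Two things could follow. The Van Elteren test could lose precision, because some of the balance built in by the allocation is not used. The by-age tables could also mislead. In the 13-or-over column, 5 mg bid is the high dose for some patients and the low dose for others, so a reader who takes that column as the 5/10 mg comparison would be wrong by however many light older patients it holds.

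**Working it through.** **1. Categories side by side** (protocol 9.1 and 10.4; SAP section 1, 7.5 and 15.1.4)

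| Patient category | Low / high dose (bid) | Grouped for dosing with | SAP stratum |
|---|---|---|---|
| 4 to <13 years | 2 / 5 mg | younger | <13 |
| ≥13 years, <25 kg | 2 / 5 mg | younger | ≥13 |
| ≥13 years, ≥25 kg | 5 / 10 mg | older | ≥13 |

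Only the middle row crosses over.

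**2. The plan's own figure.** The documents give no power calculation for the CIC. The primary-endpoint figure of 34 per group reproduces (two-sample t-test, difference 10, SD 12.5, two-sided 0.05, 90% power: 33.8, rounded up to 34; power at 34 is 90.2%), but it has no bearing on this point.

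**3. How many patients.** The share in the middle row is not stated, so it is assumed. Of 129 patients:
- 5%: 0.05 × 129 = 6
- 10%: 13
- 20%: 26
- 30%: 39

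If the remaining patients split evenly between the other two rows, a 20% share makes the light patients 20/(20 + 40), one third of the 13-or-over stratum.

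**4. Effect on the test, by simulation.** Assumptions:
- 43 high-dose and 43 placebo patients (the planned group size), randomised 1:1 within each dosing group; patients outside the light older group split evenly between the other two rows.
- A normal latent outcome with SD 1, cut into seven categories.
- 6,000 runs per setting, with both choices of strata applied to the same data.

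Within a stratum of size n, with n1 treated, the score is rank/(n+1). U is the sum of treated scores minus n1 times the mean score. V = n1(n − n1)/[n(n − 1)] × Σ(score − mean)². Reject when |ΣU/√ΣV| > 1.96.

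Each cell shows age strata / dosing-group strata:

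| Share | Type I, no shift | Type I, 0.5 SD shift in light older patients | Power, 0.6 SD effect in all | Power, unequal effects |
|---|---|---|---|---|
| 5% | 0.049 / 0.051 | 0.050 / 0.050 | 0.720 / 0.720 | 0.717 / 0.724 |
| 10% | 0.052 / 0.052 | 0.048 / 0.049 | 0.727 / 0.728 | 0.681 / 0.691 |
| 20% | 0.051 / 0.051 | 0.048 / 0.050 | 0.726 / 0.730 | 0.649 / 0.668 |
| 30% | 0.051 / 0.053 | 0.046 / 0.047 | 0.715 / 0.718 | 0.609 / 0.626 |

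The last column assumes effects of 0.4 SD in both 2/5 mg categories and 0.8 SD in the 5/10 mg category, with a 0.5 SD outcome shift in the light older patients. It is chosen to be unfavourable to the age strata. The differences there are 0.7, 1.0, 1.9 and 1.7 points; with equal effects they are under half a point. The simulation error of one power estimate is about √(0.7 × 0.3/6000) = 0.6 points.

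**5. Three strata instead of two.** Protocol 10.4 lists the three categories separately, so the check was repeated with one stratum per row. Against the age strata this loses 0.2 to 0.5 points with equal effects and gains 0.6 to 2.7 points with unequal effects.

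**The case against.** The best defence is that age strata are a prespecified and legitimate choice. Protocol and SAP agree on them, and SAP 3.3 reports no change from the protocol. Age is a baseline variable, and under protocol 10.4 each age/weight category is randomised 1:1:1, so allocation is also 1:1:1 in expectation among all patients aged 13 or over.

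The dose-mixing argument can also be turned round. SAP section 1 defines high dose as an age- and weight-adjusted dose, and the lower doses were chosen to give exposures similar to those in the older patients. Every main comparison pools 5 and 10 mg bid as high dose. Strata by dosing category would instead put light teenagers or adults beside four-year-olds. The success rule needs only direction on the CIC, the subgroups carry no inferential statistics, and the listings in SAP section 8 separate the four dose labels.

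Most of this stands, and it is why the point is minor. It does not explain why the analysis leaves out part of the rule that set the allocation. Nor do patient listings replace a summary table whose columns match the dose pairs. The CIC test is also second in the confirmatory sequence, so its strata deserve some care.

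**Conclusion.** The mismatch is real and its consequence is small. Under assumed shares of 5% to 30%, moving the light older patients to the younger stratum changes CIC power by about 0 to 2 points and leaves type I error at 0.046 to 0.053 throughout. The other loss is clarity in the subgroup tables. These figures rest on assumed shares, effects and outcome shift. They do not model the period described in SAP section 1 when younger patients under 18 kg went only to 2 mg bid or placebo and those of 18 kg or more only to 5 mg bid or placebo. The number randomised under that scheme is not given.

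Three stronger readings are not supported:

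- A reader might infer that the test is biased or that patients sit in a wrong stratum. Age strata are valid under the current 1:1:1 allocation, and the SAP follows the protocol. The 6 to 39 patients in step 3 are illustrative, not a count of errors.
- A reader might infer a second mismatch from dates, since the general age formula in SAP 6.5 counts to informed consent while "Randomization will be on Day 1 at the start of dosing" (protocol 9.2.3). Neither document says on which date the IWRS takes age. With four weeks of screening and an assumed 20-year age span, 4/52/20 = 0.38%, and 0.0038 × 129 = 0.5 patient would be affected.
- A reader might infer that the primary MMRM needs a category factor. It already adjusts for continuous age, and nothing here shows a defect in it.

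**What to change.** Before unblinding:

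- Stratify the Van Elteren test by the age/weight category held in the IWRS: (4 to <13 years, or ≥13 years and <25 kg) versus (≥13 years and ≥25 kg). Keep the age-only strata as a sensitivity analysis, or do the reverse. Confirm from the IWRS specification whether allocation used two or three categories.
- Change protocol 15.2.6 (and its synopsis counterpart) and SAP 15.1.4 together, so that the two documents do not conflict and SAP 3.3 remains true.
- In SAP 7.5 and Appendix 4, add descriptive tables by this category beside those by age.
- Report how many patients change stratum, by treatment group.
- State how many patients were randomised under the temporary 18 kg scheme, because two age/weight strata do not reproduce that allocation.

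The cost is a short wording change in both documents, one extra run of the test and one more set of descriptive tables. No new data are needed.

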15.2. SECONDARY EFFICACY

The secondary efficacy analyses described in SAP section 15.2.1.1 will be performed for the ITT population with LOCF imputation. Efficacy analyses described in SAP section 15.2.1.2, 15.2.1.3, 15.2.1.4, 2 and 15.2.1.5 will be performed for the ITT population.

15.2.1 SECONDARY EFFICACY VARIABLES & DERIVATIONS

Change from baseline calculation will be done as defined in section 6.5.

15.2.1.1 Change from Baseline in Total Score of Caregiver Top 3 Concerns at Week 24

The severity of patient symptoms will be assessed using the Caregiver Top 3 Concerns scale, which uses a 100-mm visual analogue scale (VAS). The caregiver will select the 3 symptoms that are most problematic at baseline from a list of 12 possible concerns, and will rate each one using the VAS to indicate the severity on a scale of 0 to 100. The

Document:	\\ieedc-vnasc01\BIOSdata\Newron\Sarizotan\PXA76395\Biostatistics\Documentation\SAP		
Author:	[name]	Version Number:	V2
		Version Date:	[30March2020]
Template No:	CS_TP_BS016 – Revision 4	Reference:	CS_WI_BS005
Effective Date:	01Apr2016		

same 3 symptoms will be rated using the VAS at the scheduled visits at Weeks 8, 16, and 24 in the double-blind treatment period. The Top 3 Concerns Total Score for each patient is calculated as the sum of the score for the 3 concerns rated. This total score can range from 0 to 300.

15.2.1.2 Mean rating of Clinical Global Impression of Change (CGI-C) at Week 24

The CGI-C rating scale permits a global evaluation of the subject's improvement or worsening over time. At each post-baseline visit, the rater will assess the change in the subject's symptoms of RTT relative to the symptoms at baseline using a 7-point scale, ranging from 1 (very much improved) to 7 (very much worse), with a score of 4 indicating no change. The CGI-C assessment will be conducted on Day 14, and at Weeks 8, 16 and 24 (or at early discontinuation) during the initial double-blind treatment period, and will be based on the patient's condition at the Baseline visit.

Improvement on CGI-C (i.e. Responder) will be defined as a Likert scale score of 1 (very much improved) or 2 (much improved) or 3 (minimally improved).

15.2.1.3 Change from baseline to Week 24 in Motor-Behavioral Assessment Scale (MBAS)

The MBAS is comprised of three sub-scales i.e. Behavioral/Social Assessment (included 16 items), Orofacial/Respiratory Assessment (included 7 items) and Motor Assessment/Physical Signs (included 14 items).

Each item is rated on a scale from 0 to 4, with '0' indicating normal or never, and '4' indicating very severe or constant.

To see the change in Motor-Behavioral Assessment Scale, change from baseline will be calculated at Week 24, considering the grand total score (all 3 sub-scales), as well as the total score on each of the three sub-scales.

Day 0 will be considered as baseline for this endpoint.

15.2.1.4 Change from baseline to Week 24 in other respiratory symptoms of RTT

The following additional respiratory parameters will be analyzed:

- Percent time spent with breathing dysrhythmia (% time apnea + % time hyperventilation) per hour;
- Number of hyperventilation episodes (≥ 10 seconds each) per hour;
- Oxygen saturation (# of episodes of oxygen desaturation below 90% per hour).
- Respiratory Distress Index - The sum of the following parameters calculated per hour of

Document:	\\ieedc-vnasc01\BIOSdata\Newron\Sarizotan\PXA76395\Biostatistics\Documentation\SAP	Version Number:	V2
Author:	[name]	Version Date:	[30March2020]

Template No: CS_TP_BS016 – Revision 4
 Effective Date: 01Apr2016

Reference: CS_WI_BS005

wakefulness: 1) number of breath-holding episodes, 2) number of episodes of hyperventilation [1 and 2 are as defined in inclusion criteria; each would have to be ≥ 10 seconds in duration], and 3) number of drops in oxygen values to $< 90\%$.

- Apnea episodes collected parallel at the hospital/clinic at Baseline and at Weeks 16 and 24, using a stretch-sensitive resistance plethysmograph (SOMNOtouch)

Data from the Bio-Radio and the SOMNOtouch will not be pooled and will be analyzed separately.

Data for determination of these additional respiratory outcome parameters was collected during home cardiorespiratory recording using the BioRadio™ and in parallel at the hospital/clinic at Baseline and at Weeks 16 and 24, using a stretch-sensitive resistance plethysmograph (SOMNOtouch) and was obtained from the vendor Vivonoetics.

To see the change in other respiratory symptoms of RTT, change from baseline will be calculated at Week 24.

15.2.1.5 Change from baseline to Week 24 in Rett syndrome Clinical Severity Scale (RCSS)

The RCSS scale will assess the severity of symptoms of RTT. This scale contain 13 items which measure and provide a clinician rating of core symptoms of Rett syndrome on a Likert scale of either 0 to 4 or 0 to 5, with a maximum total score of 58.

The change in RCSS, will be determined by calculating the difference between baseline and Week 24 for the total score of RCSS . Day 0 will be considered as baseline for this endpoint.

